Therefore, in order to investigate the impact of face coverings on exercise capacity, research will take place in two phases:

Phase I: Participants will be randomized and complete 2 treadmill trials including (1) cardiopulmonary exercise tests (CPET) with face covering, and (2) CPET without face covering.

Phase II: Participants will be randomized and will complete 2 cycle ergometer trials including (1) cardiopulmonary exercise tests (CPET) with face covering, and (2) CPET without face covering. Cognitive testing will occur incrementally as exertion increases.

SPECIFIC AIMS & OUTCOMES

Phase I:

The proposed study consists of 4 specific aims:

Specific Aim 1: Describe the primary and secondary outcomes of athletes during a Cardiopulmonary Exercise Test (CPET) on a treadmill with (arm 1) and without (arm 2) the use of a face covering.

Specific Aim 2: Conduct a randomized crossover trial to determine if there is a significant difference in maximal and submaximal aerobic exercise capacity (VO₂ max; assessed during the CPET) in athletes with (arm 1) and without (arm 2) the use of a face covering.

Specific Aim 3: Describe participants' experiences' while wearing a face covering during exercise.

Specific Aim 4: Determine reliability of the Attitudes Toward Face Coverings Questionnaire

Primary Outcomes:

- VO₂ max during treadmill Cardiopulmonary Exercise Testing (CPET)
- Test duration (time) on a CPET

Secondary Outcomes

- Minute ventilation (VE) at max during CPET

- Subjective dyspnea rating (Borg) at max during CPET
- Subjective exertion rating (Borg) at max during CPET
- O₂ saturation at baseline, each stage, and recovery during CPET
- Blood pressure at baseline, each stage, and recovery during CPET
- Max heart rate during CPET
- Respiratory quotient at max during CPET
- Attitudes Toward Face Coverings Questionnaire
- Scale of Measuring Subjective Perceptions Questionnaire

Phase II:

Specific Aim 1: Describe the primary and secondary outcomes of participants during a Cardiopulmonary Exercise Test (CPET) on a cycle ergometer with (arm 1) and without (arm 2) the use of a face covering.

Specific Aim 2: Conduct a randomized crossover trial to determine if there is a significant differences in cognitive performance outcomes in participants with (arm 1) and without (arm 2) the use of a face covering. Cognitive performance will be measured by simple reaction time and accuracy on the SRT task.

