Specific Aim 3: Describe differences in outcomes between participants with and without previous history of COVID-19 diagnosis

Primary Outcomes:

- VO₂ max during CPET
- Test duration (time) on a CPET
- Reaction time (measured in milliseconds) and percentage accuracy on the SRT task

Secondary Outcomes:

- Minute ventilation (VE) at max during CPET
- Subjective dyspnea rating (Borg) during CPET
- Subjective exertion rating (Borg) during CPET
- O₂ saturation at baseline, each stage, and recovery during CPET
- Blood pressure at baseline, each stage, and recovery during CPET
- Max heart rate during CPET
- Respiratory quotient at max during CPET
- Blood lactate during CPET

[figure not shown]
INVESTIGATIONAL PLAN

Research Design and Methodology

Phase I:

In this prospective, randomized crossover trial of eligible athletes, we will compare VO₂ max during two maximal cardiopulmonary stress exercise tests (CPET), seven to ten days apart. Subjects will be randomized into either the face covering or non-face covering group using a 1:1 randomization scheme, stratified by sex, and will serve as their own control in the subsequent test seven to ten days later (see Figure 1. Randomization diagram, below). A within-subjects analysis will be performed stratified by sex.

[figure not shown]
Figure 1. Phase I Randomization diagram

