**Phase II:**

In this prospective, randomized crossover trial of 50 eligible participants, we will compare two maximal cardiopulmonary stress exercise tests (CPET) on a cycle ergometer, seven to ten days apart, and the impact on cognitive performance. ECG monitoring will take place during exercise testing among individuals with history of COVID-19. Subjects will be randomized into either the face covering or non-face covering group using a 1:1 randomization scheme, stratified by prior COVID-19 diagnosis, and will serve as their own control in the subsequent test (see Figure 2. Randomization diagram, below). A within-subjects analysis will be performed stratified by sex.

Cognitive testing will take place at the end of each stage of the CPET. Cognitive testing using the SACL Cognition application on iPad will include a baseline SRT measurement and additional measurements at the end of each stage of the CPET. The baseline will include a 30s session of SRT for familiarization and then a 30s session will be scored. SRT will then be administered for 30s at the end of each stage of the CPET. The SRT task includes a visual stimulus presented on the touchscreen. Subjects will be instructed to press the stimulus on-screen as quickly as possible. Reaction time and accuracy will be measured on the SRT task. Reaction time is calculated as the average amount of time in seconds between stimulus presentation and user response within a session. Accuracy is calculated as the total number of correct responses to stimuli divided by the total number of stimuli presented during a session (presented as a percentage).

Figure 2. Phase II Randomization diagram

Phase I: Eligibility Criteria

Inclusion Criteria	Rationale
18-29 years of age	Younger and older individuals are excluded to reduce variability of lung volume outcomes. Herdy, A. H. & Uhlendorf, D. (2010) Reference values for cardiopulmonary exercise testing for sedentary and active men and women. Sociedade Brasileira de Cardiologia.

Exclusion Criteria	Rationale
Orthopedic or neurologic, or other limitations	Individuals with limitations that would not allow for exercise testing on a treadmill are excluded.
Previous or current diagnoses for cardiopulmonary conditions	Individuals with conditions for which a healthcare provider has discouraged high-intensity exercise are excluded (e.g., arrhythmia, pacemakers, Wolfe Parkinson White syndrome).

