Presence of beards	Beards interfere with the fit of the Vo2 mask. Therefore, participants with beards will be asked to shave prior to their visit. If they are unwilling to shave, they will not be eligible for the study.
Claustrophobia	Participants who have been diagnosed or treated for claustrophobia will be excluded. Claustrophobia is a contraindication of the CPET test.
Currently experiencing symptoms of COVID-19 or < 7 days since last symptoms	Participants will be screened for COVID-19 symptoms using the BSW COVID-19 screener; if participants have past history of COVID-19 based on laboratory testing, participants will be ineligible if <7 number of days since last symptoms

Study Procedures

Phase I & II Subject Recruitment

Up to 100 participants (50 for each phase) will be recruited from Baylor Scott & White Sports Therapy and Research at The Star in Frisco, Texas through approved fliers, calls, emails, and social media, as well as through local community organizations, healthcare clinics, and collaborating centers and organizations, including but not limited to the Sports Academy and the University of North Texas. IRB-approved fliers will be posted at BSW The Star and at affiliated organizations and collaborators in the DFW Metroplex and surrounding areas. In addition, members of the study team will attend meetings with local clinicians and community partners to inform them of the purpose of the study. The study flier will contain information on the study and methods to contact the study team including (1) a QR code linked to the eligibility screener which will be stored in a REDcap, a HIPAA-compliant (21 CFR Part 11) secure web application, (2) a phone number, and (3) an email address of the study coordinator. Interested individuals may contact the study team by phone or email to learn more about the study and undergo a telephone screener or follow the QR code to complete the eligibility screener electronically. A snowball sampling technique will be used for further recruitment whereby interested participants will be invited to ask other athletes they know to contact the study team about participation. Eligible individuals will be contacted by a member of the study team to schedule their first study visit. It is anticipated that recruitment will take 2-4 weeks during each phase to achieve our desired sample size.

Subject Information and Screening

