Eligible individuals will be screened by trained study coordinators via telephone using the Eligibility Script. If a participant is ineligible based on the screening tool, they will be thanked for their time and informed that they are not able to participate further. If a participant is eligible based on the screening tool, they will be asked to schedule a baseline assessment appointment where informed consent will be obtained. All individuals will be given a screening ID number and all screening information will be input into a password-protected subject tracking database.

COVID-19 Screening

Participants will be instructed to wear face coverings from the parking lot and inside the building. Prior to participation in the CPET, subjects will complete the BSWH COVID-19 screening (procedure outlined in supplementary materials) and a temperature check with a TIR-1 thermometer (procedure outlined in supplementary materials) outside of testing environment. If the subject screens positive or has a temperature of over 100 degrees, subject will not be able to participate in the study and instructed to leave the facility and

comply with current state and local recommendations. If the subject screens negative on both assessments, subject will be taken into testing area for CPET testing.

Informed Consent

Informed consent will be obtained by study staff in person at the beginning of their study visit and prior to any study related procedures taking place. Informed consent will be conducted in a private location using similar procedures as described above by trained study staff to minimize coercion. Participants will be informed about the study, have sufficient time to review the consent form, and all study questions will be answered prior to signature. Participants will be given sufficient opportunity to decide whether or not they want to participate. If the participant elects to enroll in the study, they will be instructed on how to sign the consent form and a copy will be given to them prior to the initiation of any study procedures.

Randomization

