A standard cycle ergometry ramp protocol⁷ will be designed for each participant as used in previous masking study.⁸ The initial workloads and incremental increases will be determined based on the subject's age and weight. The protocol consists of 1 minute of unloaded cycling, followed by a 2-minute warmup at 25 W. The exercise phase consists of continuous progressive increases in power output (25 W · min⁻¹) every three minutes until the subject is unable to maintain 50 rpm. This is followed by 4 min of active recovery at 20 W.

- The Borg Rating of Perceived Exertion (6-20) scale will be used during the test to assess subjective exertion
- The Modified Borg Dyspnea Scale (0-10) will be used to assess subjective shortness of breath.
- Intermittent blood pressure measurements and pulse oximeter measurements will be taken by an exercise physiologist and heart rate will be monitored constantly.
- Blood lactate will be measured pre and post-CPET using a Nova Medical Lactate Plus: Blood Lactate Measuring Meter-Version 2 device.

Testing will be terminated if any of the following occurs: (a) subject becomes symptomatic; (b) pain is reported; (c) subject wishes to terminate test; (d) unsafe drop in blood pressure or hypertension over 250/120 mmHg reported; or (e) subject reports a “20” on Borg RPE scale or “10” on Dyspnea scale. Other termination of the test is reserved for the clinical judgment of research staff to ensure safety of the subject. After termination of the test, subject will be instructed to perform a cycling cool-down of 3 to 5 minutes. After subject has completed cool-down, recovery blood pressure, heart rate and pulse oxygenation will be measured and recorded. After completion of the first test, subject will be scheduled for second CPET 7-10 days later to allow for adequate recovery. When data collection is complete, CPET data will be gathered from metabolic cart and matched with subject testing materials.

Disinfection Procedures

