Participant characteristics will be summarized with means and standard deviations or medians and interquartile ranges for numerical variables, and counts and percentages for categorical variables. The primary outcomes, VO₂ max and test duration, will first be assessed for normality using a Kolmogorov-Smirnov test prior to determining the analysis to be used. If the distribution meets the normality assumption, paired t-tests will be used to determine if there is a difference between participants when wearing and not wearing a face covering. If the distribution does not meet the normality assumption, Wilcoxon signed-rank tests will be used. All secondary outcomes will follow the same analysis plan of assessing the normal distribution assumption to determine the appropriate test for each outcome. Inter-rater reliability analysis will be conducted for the Attitudes for Face Coverings Questionnaire. All analysis will be performed using SAS 9.4 at a 0.05 significance level.

Risks & Benefits

- Physical risks: The potential risks include any and all risks associated with exercise including muscular injury, increased blood pressure and heart rate, and cardiac arrest. Other risks include hypoglycemia post-exercise and lightheadedness or syncope. Although some risks are unavoidable, the careful monitoring of signs and symptoms by the subject and clinical staff will minimize these risks.
- No psychological risks have been identified by participating in this study.
- No social risks have been identified by participating in this study.
- No economic risks have been identified by participating in this study.
- No legal risks have been identified by participating in this study.
- Potential benefits: Participants in this study may experience greater confidence in performing aerobic activities and may gain a better understanding of their personal functional exercise capacity at the time of testing. Participants may also better understand their body's response to exercise with and without a face covering which may impact training and performance in recreational and occupational ventures.

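### Baseline blood pressure and SpO2 are listed among the tested outcomes, no analysis uses the same-visit resting values as covariates, and SRT, a Phase II primary, has no named analysis

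*Combined protocol and SAP*

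**What the plan says.** **Collection.** The CPET procedures for both phases record resting blood pressure and pulse oximetry before the test, and Phase II adds resting lactate. The Phase II procedures state "Blood lactate will be measured pre and post-CPET". Under Research Design and Methodology, Phase II, "Cognitive testing using the SACL Cognition application on iPad will include a baseline SRT measurement", followed by a scored session at the end of each stage.

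**Outcomes.** Under Specific Aims & Outcomes, both phases list as a secondary outcome "Blood pressure at baseline, each stage, and recovery during CPET", with a matching item for oxygen saturation. Phase II also lists "Blood lactate during CPET". SRT reaction time and accuracy are Phase II primary outcomes.

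**Analysis.** The Data Analysis section names VO2 max and test duration as the primaries. It prescribes a normality check followed by a paired t-test or a Wilcoxon signed-rank test, and then says "All secondary outcomes will follow the same analysis plan of assessing the normal distribution assumption to determine the appropriate test for each outcome". It adds: "All analysis will be performed using SAS 9.4 at a 0.05 significance level". Research Design and Methodology adds only that the within-subjects analysis is stratified by sex. No covariate, change score, ANCOVA or repeated-measures model appears anywhere.

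**The concern.** Two things follow if the outcome list and the analysis rule are read together.

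First, baseline blood pressure and SpO2 become tested outcomes. A comparison of values taken before exercise does not address the effect of a covering during exercise. If the values also precede fitting of the covering, the treatment cannot have acted on them, and each test only adds a 5% chance of a false positive.

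Second, information already collected goes unused. Pairing removes stable differences between people. It does not remove a shift in a person's resting state between two visits seven to ten days apart. The same-visit resting value may carry that information. At stake is the precision of the stage and recovery values of blood pressure and SpO2, of post-test lactate, and of SRT. SRT matters most because it is a primary outcome for which the sponsor still has to write an analysis.

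**Working it through.** **The plan's own figure.** Recruitment is stated as "Up to 100 participants (50 for each phase) will be recruited". No effect size, SD, within-person correlation or power is given, so this number cannot be reproduced. As a reference point, a paired t-test with n = 50 and two-sided 0.05 (sidedness is not stated; two-sided assumed) has 80% power for a difference of 0.404 SD of the paired differences, by the noncentral t. The normal approximation agrees: (1.960 + 0.842)/√50 = 0.396.

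**Effect of adjustment.** Regress the within-person outcome difference (masked minus unmasked) on the within-person baseline difference. Let r be the correlation of these two differences. Relative to the unadjusted paired comparison,

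variance ratio = (1 - r²)(n - 2)/(n - 3) = (1 - r²) × 48/47 for n = 50.

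Both r and the effect sizes are assumptions. Power of the unadjusted test is 80% at 0.404 SD and 0.68 at 0.35 SD.

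| r | Variance ratio | Change | Adjusted power at 0.404 SD | Adjusted power at 0.35 SD |
|---|---|---|---|---|
| 0 | 1.021 | +2% | 79.1% | 0.67 |
| 0.15 | 0.998 | about 0% | not computed | 0.68 |
| 0.3 | 0.929 | -7% | 82.8% | 0.71 |
| 0.5 | 0.766 | -23% | 89.2% | 0.79 |
| 0.6 | 0.654 | -35% | 93.4% | 0.85 |

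Break-even is where 1 - r² = 47/48, so r = √(1/48) = 0.14. At r = 0.5 the gain is worth 50/0.766 = 65 participants in place of 50.

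**Simulation check.** In 20,000 simulated trials per setting, unadjusted versus adjusted power at 0.404 SD was 80.6% versus 83.0% at r = 0.3, and 80.2% versus 89.1% at r = 0.5. Type I error of the adjusted test was 5.0% to 5.1%. These figures leave out the period term and assume complete pairs.

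**Plain change scores.** With equal SDs, subtracting the baseline gives a variance ratio of 2 - 2r. This is 1.4 at r = 0.3 and 1.0 at r = 0.5, so change scores are worse than the unadjusted comparison below r = 0.5.

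**Timing of the baseline.** Suppose the resting value is taken with the covering on and the covering shifts it by 0.4 SD (an assumption). Adjustment then removes about r × 0.4 from the effect: 0.404 - 0.12 = 0.28 at r = 0.3, and 0.404 - 0.20 = 0.20 at r = 0.5.

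**Baseline tests.** If two baseline tests (SpO2 and blood pressure) are run on values that treatment cannot affect, and they are independent, the chance of at least one false positive is 1 - 0.95² = 9.8% per phase.

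**The case against.** The strongest objection is that the documents do not say whether resting values and baseline SRT precede fitting of the covering. The Randomization section keeps the assignment concealed only until consent is complete, so it may be known before the resting measures. The COVID-19 Screening section says "Participants will be instructed to wear face coverings from the parking lot and inside the building", but this does not settle what is worn when they are recorded. If the covering is already on, the baseline is a post-treatment value. Adjusting for it would then bias the total effect, and a test of it would be an interpretable at-rest comparison. This stands as a condition: adjustment is sound only if the order of steps is fixed first.

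Sealing the Visit 1 assignment does not help at Visit 2, when the participant knows which condition remains. Anticipation could shift resting blood pressure or SRT, and adjustment would remove part of that response. This limitation also stands.

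The gain rests on r, for which the documents give no value, and below about 0.2 there is almost none. The count of 50 pairs is also optimistic for later stages, because tests end at different times. Both points stand.

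A reader might infer that the plan prescribes an unadjusted test at every time point. It does not. It is silent on how the time points of one outcome are handled, so this is only the default reading. Nor does the quoted rule cover SRT: it governs secondary outcomes. The gap there is a missing analysis, which is more serious than a missing covariate. Repetition of baseline SRT at Visit 2 is implied by the design text, but SRT is absent from the Phase II Schedule of Assessments.

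**Conclusion.** The point holds in a limited form and should be acted on. Baseline blood pressure and SpO2 are listed as outcomes that fall under the paired-test rule. The collected resting values have no stated role as covariates, and SRT has no named analysis. The consequence is a possible loss of precision: with 50 complete pairs, adjustment costs about 2% of variance if the baseline is uninformative, breaks even near r = 0.14, and saves 7%, 23% and 35% at r = 0.3, 0.5 and 0.6. These figures assume baselines taken before the covering is fitted.

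Three stronger conclusions might be inferred, and the documents do not support them. The unadjusted paired comparisons are not invalid. Post-test lactate compared without its pre-test value is a legitimate result, although the listed timing needs to match the samples taken. The main exercise-capacity comparison is not weakened, because VO2 max and test duration have no baseline counterpart.

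**What to change.** 1. Take resting blood pressure, SpO2, pre-test lactate and baseline SRT at both visits before the covering is fitted, with the Visit 1 assignment still sealed. State that baseline SRT is repeated at Visit 2, and add SRT to the Phase II Schedule of Assessments.
2. Remove baseline values from the tested outcomes and report them descriptively by condition.
3. For stage, recovery, post-test lactate and SRT outcomes, estimate the masked-minus-unmasked difference adjusted for the within-person baseline difference and for period (through the sequence term), with a 95% CI. Do not use plain change scores.
4. Name this explicitly as the analysis of the SRT primary outcome.
5. Prespecify a rank-based or robust version for clearly non-normal or bounded outcomes, such as SpO2 and SRT accuracy.
6. Define the lactate outcome as post-CPET lactate adjusted for pre-CPET lactate.

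The cost is SAP wording, a fixed order of steps at each visit, and about one degree of freedom for the baseline (about 2% of variance if it is uninformative). The period term uses one more. No new measurement is needed beyond confirming the Visit 2 baseline SRT.
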